**Figure 2. Modified Intent-to-Treat (mITT) Analysis**

**6.3 Per Protocol (PP)**

- a) **Definition:** The PP population includes any infant that was enrolled, randomized and did not have any major protocol violations for analysis as determined by the study investigators. See Appendix 1.
- b) **Analysis:** For the PP analysis, study outcomes will be included in the analysis as follows:
  - i) **Vaccinated group:** study outcomes in the 48-hour monitoring after vaccination. The analysis will exclude infants who do not receive vaccine by 12 hours.
  - ii) **Unvaccinated group:** study outcomes in the 48-hour monitoring period after randomization. The analysis will exclude infants who are vaccinated during the study period.

## 6.4 Analysis of populations

The mITT population will be the primary analysis population for all planned analyses for the study objectives. The ITT population will be analyzed for the primary objective. The PP population will be analyzed for all planned objectives as supporting analyses. For comparison, pre-specified secondary analyses will also be performed using the ITT and PP populations.

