5 STUDY SCHEDULE, PROCEDURES, & EVALUATIONS

5.1 Study day definitions

Table 3. Study Day definitions		
	Vaccinated group	Unvaccinated group
Day 1	R → V + 23:59 hours:minutes	R → R + 23:59 hours:minutes
Day 2	V + 24 hours → V + 47:59 hours:minutes	R + 24 hours → R + 47:59 hours:minutes
Day 3	V + 48 hours → V + 95:59 hours:minutes	
Day 4	V + 96 hours → V + 119:59 hours:minutes	
Day 5	V + 120 hours → V + 143:59 hours:minutes	
Day 6	V + 144 hours → V + 167:59 hours:minutes	
Day 7	V + 168 hours → V + 191:59 hours:minutes	
Day 8	V + 192 hours → V + 215:59 hours:minutes	
Day 9	V + 216 hours → V + 239:59 hours:minutes	
Day 10	V + 240 hours → V + 263:59 hours:minutes	
Day 11	V + 264 hours → V + 287:59 hours:minutes	
Day 12	V + 288 hours → V + 311:59 hours:minutes	
Day 13	V + 312 hours → V + 335:59 hours:minutes	
Day 14	V + 336 hours → V + 359:59 hours:minutes	

R = time of randomization. V = time of vaccination. If infants in the vaccinated group are not vaccinated, then “V” should be replaced by “R + 12 hours”. Note that for vaccinated group, “Day 1” will be longer than 24 hours.

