6.6 Analysis Plan

6.6.1 Pilot Study

The pilot phase of the study will include 12 infants. There will not be any formal analysis of study data. However, the feasibility benchmarks listed in **Table 5** will be documented for the first 12 patients to assess protocol adherence. These subjects will contribute to the final sample for analyses in the study objectives.

Table 5: Benchmarks for Pilot	
Benchmark	Target
Among pre-screened and eligible, LARs approached for consent	70%
Among approached for consent, consent obtained	40%
Documentation of reason for non-consent (of those approached)	80%
Among consent obtained, percent randomized	80%
Administration of vaccines in the vaccination group within 6 hours of randomization	60%
Administration of vaccines in the vaccination group within 12 hours of randomization	80%
Entire 48-hour monitoring period assessed for apnea events	80%

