**Figure 1. Intent-to-Treat (ITT) Analysis**

**6.2 Modified Intent-to-Treat (mITT) population (Figure 2)**

- a) **Definition:** The definition is the same for the ITT and mITT. The mITT population includes any infant that was enrolled and randomized in the study.
- b) **Analysis:** For the mITT analysis, infants will be analyzed in their assigned treatment arms irrespective of receipt of vaccine. Study outcomes will be included in the analysis as follows:
  - i) **Vaccinated group:** study outcomes in the 48-hour monitoring after vaccination. If vaccination does not occur by 12 hours after randomization, then study outcomes will be assessed between 12 and 60 hours after randomization.
  - ii) **Unvaccinated group:** study outcomes in the 48-hour monitoring period after randomization. This is the same for the IIT and the mITT populations.

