## 8 ANALYSIS OF STUDY OBJECTIVES

For each objective below the analysis using the primary mITT population is described. Secondary analyses will also be done using the ITT and PP populations as described in Section 6.

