proportions will be compared using a Mantel-Haenszel statistic in a stratified analysis by study site and gestational age to control for the randomization blocks. The stratified odds ratio and corresponding 95% confidence interval for the occurrence of these outcome measures will also be calculated. We will provide a listing of SAE narratives and relatedness descriptions.

- c) The third exploratory objective (**EO-3**) is to compare clinically important adverse events occurring between 48 hours and 14 days after vaccination among infants in the vaccinated group who do / do not have apnea in a 48-hour monitoring period after vaccination.

For this objective the proportion of infants in the vaccinated group with and without apnea in a 48-hour monitoring period who experience each of the clinically important adverse events listed below at least once between 48 hours and 14 days after vaccination will be presented.

- $\geq 1$  episode of clinical apnea in hospitalized infants (EOM 3.1)
- any increase in respiratory support in hospitalized infants (EOM3.2)
- blood culture and/or antibiotics (intravenously or intramuscularly) in the setting of blood culture for sepsis evaluation in hospitalized infants (EOM 3.3)
- positive pressure ventilation in hospitalized infants (EOM 3.4)
- readmission to the hospital within 14 days of vaccination in discharged infants (EOM 3.5)

These subgroup comparisons will be made using a Mantel-Haenszel statistic in a stratified analysis by study site and gestational age to control for the randomization blocks at the two-sided alpha 0.05 level. The stratified odds ratio and corresponding 95% confidence interval for the occurrence of these outcome measures will also be calculated.

No adjustments will be made to the alpha level (two-sided alpha=0.05) for these exploratory analyses.

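### The primary analysis set for Exploratory Objective 3 (mITT) does not match its question about events after vaccination, and may bias the association

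*SAP*

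**What the plan says.** SAP 8.3(c) sets EO 3 to "compare clinically important adverse events occurring between 48 hours and 14 days after vaccination among infants in the" vaccinated group, split by whether the infant had apnea in the 48 hours after vaccination. The test is a Mantel-Haenszel comparison stratified by site and gestational age, with an odds ratio and 95% confidence interval.

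The analysis set comes from SAP 6.4: "The mITT population will be the primary analysis population for all planned analyses for the study objectives". The opening of SAP section 8 repeats the default without an exception for EO 3: "For each objective below the analysis using the primary mITT population is described".

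SAP 6.2 defines that set by randomization alone ("The mITT population includes any infant that was enrolled and randomized in the study") and says that "infants will be analyzed in their assigned treatment arms irrespective of receipt of vaccine". Its timing rule is: "If vaccination does not occur by 12 hours after randomization, then study outcomes will be assessed between 12 and 60 hours after randomization". The note to the study-day table in Protocol 5.1 adds a clock for infants who never receive vaccine: "If infants in the vaccinated group are not vaccinated, then" V is replaced by R + 12 hours.

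SAP 6.4 also plans a per-protocol (PP) analysis of every objective as supporting. SAP 6.3 and Appendix 1 exclude from it infants not vaccinated by 12 hours.

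**The concern.** Analysis as assigned is valuable because it preserves a randomized comparison. EO 3 compares infants with apnea to infants without it inside one arm, so there is no randomization to preserve. Keeping infants irrespective of vaccine receipt only adds infants to whom the question does not apply.

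Two kinds of infant are affected. A never-vaccinated infant enters with a substitute vaccination time. An infant vaccinated after 12 hours is classified for apnea on a window starting before vaccination; if vaccination comes after 60 hours, the whole window precedes it. The start of the later follow-up window (48 hours to day 14) for these late-vaccinated infants is not clearly stated.

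If vaccine is held back because an infant has become unstable, that infant may have both apnea in the window and later events, neither of which follows vaccination. The result could be read as apnea after vaccination predicting later harm. The mechanism is foreseeable from the protocol's own background: section 1.1 says clinicians tend to vaccinate when an infant is stable, and section 1.2 says they often delay because of concern about apnea. The trial is open-label.

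**Working it through.** **The plan's own figure.** No power or precision is stated for EO 3. The only sample size calculation concerns the primary comparison (SAP 4.2: 15% vs 30%, 135 per group, two-sided 0.05). The pooled proportion is 0.225, so the null SE is √(2 × 0.225 × 0.775 / 135) = 0.0508. The alternative SE is √((0.15 × 0.85 + 0.30 × 0.70) / 135) = 0.0500. Then z = (0.15 − 1.96 × 0.0508) / 0.0500 ≈ 1.01, which gives power 84.3%, as stated. With 10% dropout, 270 / 0.9 = 300. This reproduces but does not bear on EO 3.

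**Inputs for EO 3.**
- Apnea in vaccinated infants: 30% (SAP 4.2).
- Later events in vaccinated infants: 20% (assumption).
- Infants not vaccinated by 12 hours: 60% apnea, 50% later events (assumptions).
- Share h not vaccinated by 12 hours: not given, so 5%, 10% and 20% are shown. The 20% is the complement of the 80% pilot benchmark in Protocol Table 5, "Administration of vaccines in the vaccination group within 12 hours of randomization". It equals 27 of 135.
- Apnea and later events are independent inside each group, so the odds ratio within each is 1.00.

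**Formula.** With a = apnea rate and e = later-event rate (subscript 0 vaccinated, 1 not):
- P(apnea and event) = (1−h)·a₀·e₀ + h·a₁·e₁
- P(no apnea and event) = (1−h)·(1−a₀)·e₀ + h·(1−a₁)·e₁

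The excess of P(apnea and event) over independence is h(1−h)(a₁−a₀)(e₁−e₀). It is zero unless the two groups differ on **both** rates.

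**At h = 0.20.**
- Apnea: 0.8 × 0.30 + 0.2 × 0.60 = 0.36.
- Apnea and event: 0.8 × 0.06 + 0.2 × 0.30 = 0.108, so 0.108 / 0.36 = 30.0%.
- No apnea and event: 0.8 × 0.14 + 0.2 × 0.20 = 0.152, so 0.152 / 0.64 = 23.7%.
- OR = (0.108 × 0.488) / (0.252 × 0.152) = 1.38.

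**At h = 0.10:** (0.084 × 0.524) / (0.246 × 0.146) = 1.23. **At h = 0.05:** (0.072 × 0.542) / (0.243 × 0.143) = 1.12.

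**Sensitivity to the assumptions.** The same formula with 30% apnea and 15% later events in vaccinated infants gives these odds ratios:

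| Infants not vaccinated (apnea / later events) | 2% | 5% | 10% | 20% |
|---|---|---|---|---|
| No sicker (30% / 15%) | 1.00 | 1.00 | 1.00 | 1.00 |
| Only apnea higher (60% / 15%) | 1.00 | 1.00 | 1.00 | 1.00 |
| Moderately sicker (45% / 30%) | 1.02 | 1.04 | 1.07 | 1.12 |
| Markedly sicker (60% / 40%) | 1.05 | 1.13 | 1.23 | 1.37 |
| Extreme (80% / 60%) | 1.16 | 1.39 | 1.73 | 2.24 |

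In 20,000 simulated unstratified Mantel-Haenszel tests with 150 assigned infants, the markedly sicker row rejects in about 6%, 8% and 13% of trials at 5%, 10% and 20%, against a nominal 5%. The extreme row rejects in 12%, 27% and 56%.

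**Precision.** At h = 0.20 and N = 135, the expected cells in the main example are 14.6, 34.0, 20.5 and 65.9. SE(log OR) = √(1/14.6 + 1/34.0 + 1/20.5 + 1/65.9) ≈ 0.40. The 95% interval around 1.38 is about 0.63 to 3.03.

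**The case against.** The strongest reply is that the plan largely contains the remedy. PP is pre-specified for EO 3, removes these infants and times the window from vaccination; SAP 7.2 reports the analysis populations by arm. That stands in part. But PP is only supporting, and Appendix 1 also removes eligibility violators and infants with an hour or more of missing monitor data. The pilot benchmark for a fully assessed 48-hour period is itself only 80%, so losses unrelated to vaccination could be sizeable.

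The design also narrows the route to bias. The treating clinician must consider the infant eligible for vaccines, several unstable states exclude the infant or delay randomization (Protocol 4.1, 4.2), and randomization is set within 6 hours of anticipated vaccination (5.6.1). The stated reasons for the timing window are logistic (5.2). This stands: non-vaccination may be rare and unrelated to illness, and the bias then slight or absent.

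A reader might infer that the pilot benchmark means the trial accepts or expects 20% not vaccinated in time. It does not: it is a feasibility target for 12 infants, about six of them in this arm, and its complement includes late vaccination. Nor does the R + 12 hours note set the clock for late-vaccinated infants; it covers those not vaccinated, and the 12 to 60 hour window comes from the mITT rule.

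**Conclusion.** The mismatch stands whatever the number of infants involved: the primary EO 3 result can include infants who were never vaccinated, or whose apnea window precedes vaccination. The resulting bias is possible, not established. It needs a non-trivial share not vaccinated by 12 hours who are higher on both early apnea and later events, and the documents report neither.

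Under the main assumptions the odds ratio is 1.12 to 1.38. Across the wider range it runs from 1.00 to 2.24, with the top value requiring extreme assumptions. The main example's bias is small against EO 3's likely precision.

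It would be tempting to conclude that the plan creates a false association, or that restricting the set would give the true one. The documents support neither. The odds ratio of 1.00 among vaccinated infants is an assumption of the example. Protocol 1.1 reports links between cardiorespiratory events and disease severity, so underlying instability can tie early apnea to later events among vaccinated infants too. EO 3 is exploratory, so this is a worthwhile refinement, not a threat to the trial's main conclusions.

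**What to change.** In SAP 6.4 and 8.3(c), make the primary EO 3 set the infants in the vaccinated arm who received the study vaccines by 12 hours after randomization. Time both the 48-hour apnea window and the 48-hour to day-14 window from actual vaccination. List infants not vaccinated by 12 hours separately, with reasons and with the clock used for each, and keep mITT as a supporting analysis. State that confounding by underlying instability remains.

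The 12-hour limit is the plan's own. It also fits the data: under Protocol 5.4, monitor capture ends 60 hours after randomization for infants not vaccinated by 12 hours, so those vaccinated later lack a full 48 hours of monitoring after vaccination.

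The cost is wording. Vaccination times and follow-up events are already collected. Reasons for non-vaccination are not named as a data item in the documents, so they may have to come from the medical record. A few infants leave an exploratory comparison, including some who were vaccinated but late.

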## 7 BASELINE DATA AND FLOW CHART

### 7.1 Presentation of Baseline Data

The following baseline data will be presented by site and vaccination group: age, birthweight, sex, gestational age (median, range and number and percentages <28 weeks and ≥28 weeks gestational age), multiple gestation, reason for preterm delivery, insurance payer status, ethnicity, race, whether sibling currently enrolled or previously enrolled in this study, and medical conditions since birth (including intraventricular hemorrhage, necrotizing enterocolitis, periventricular leukomalacia, seizures, and apnea of prematurity), postnatal age on the day of randomization, postmenstrual age on the day of randomization, respiratory support and supplemental oxygen use on the day of randomization, caffeine use on the day of randomization, and receipt of Synagis or other procedures during the study period. Summary statistics (e.g., mean, median, standard deviation, interquartile range) will be presented for continuous variables. Categorical variables will be described with frequencies and percentages.

### 7.2 Flow Chart

The number of enrolled participants will be presented in a flow chart by study site and vaccination group. The number of infants with complete cardiorespiratory monitoring data for the required length of monitoring will be presented, along with a breakdown of the analysis populations by arm.

## 8 ANALYSIS OF STUDY OBJECTIVES

For each objective below the analysis using the primary mITT population is described. Secondary analyses will also be done using the ITT and PP populations as described in Section 6.

### 8.1 Primary Objective

The primary objective (**PO-1**) of the study is to compare proportions of preterm infants with apnea in a 48-hour monitoring period after vaccination in the “vaccinated” group versus a 48-hour monitoring period after randomization in the “unvaccinated” group.

- *Research hypothesis: the proportion of infants with apnea will be higher in the “vaccinated” group compared to the “unvaccinated” group.*

The proportion of infants with ≥1 apneic event will be presented for each group and compared using a Mantel-Haenszel statistic in a stratified analysis by study site and gestational age to control for the randomization blocks at the two-sided alpha 0.05 level. The stratified odds ratio and corresponding 95% confidence interval for the occurrence of apnea will also be calculated.

Apnea will be defined as a pause in respirations of >20 seconds, or a pause in respirations of >15 seconds with associated bradycardia (heart rate <80 beats per minute), obtained from the cardiorespiratory monitor. Presence of ≥1 apneic event will be counted as positive (1) for this analysis and no apnea reported will be negative (0). Apneic events identified by the

cardiopulmonary monitor will be confirmed during manual blinded review via an agreed-upon review process. Apneic events determined by the monitor must also be confirmed by manual review to be counted as apnea for the primary analysis. If these events are NOT by manual review, then they are not counted as apnea for the primary analysis. However, events without supporting cardiorespiratory monitoring strips, that cannot be manually reviewed, will also be counted as apnea for the primary analysis.

No adjustments will be made to the alpha level (two-sided  $\alpha=0.05$ ) for the primary objective.

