DTwP+Hib ²¹	Prospective observational	97	27	12%	72 hours	Lower weight More severe apnea of prematurity Chronic lung disease
DTwP, Hib, HBV ²²	Prospective observational	79	28	30%	24 hours	N/A
DTaP, IPV, Hib ²³	Retrospective observational	78	28	47%	48 hours	Severe clinical course Persistence of cardiorespiratory symptoms at time of immunization
DTaP, IPV, Hib, HBV ²⁴	Retrospective	53	28	13%	72 hours	N/A
DTaP ¹²	Randomized controlled	191	27	“Prolonged apnea” 16%: DTaP group 20%: control group	48 hours	N/A
DTaP, IPV, Hib, HBV ²⁵	Prospective observational	45	27	11%	72 hours	Chronic diseases
Multiple, including HBV, DTaP, Hib, OPV ²⁶	Retrospective	411	27	5%	7 days	Previous sepsis Longer prior duration of CPAP
Multiple, including HBV, DTaP, Hib, IPV, OPV, Strep pneumo, influenza ²⁷	Retrospective	497	Not provided	13%	48 hours	Younger postnatal age Lower birth weight More severe clinical illness

DTaP, IPV, Hib or DTwP, IPV, HiB ²⁸	Retrospective	124	27	45%	72 hours	Lower weight
DTaP, Hib, meningococcal serogroup C ²⁹	Retrospective	76	27	38%	24 hours	N/A

DTwP=diphtheria, tetanus, whole cellular pertussis; DTaP=Diphtheria, tetanus, acellular pertussis; HBV = hepatitis B virus; Hib = *Haemophilus influenzae* type B; IPV=inactivated poliovirus; OPV=oral poliovirus.

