### 4.2 Sample Size and Power

The study has approximately 84.3% power to reject the null hypothesis of no difference in the proportion of infants with apnea in the “vaccinated” group compared to the “unvaccinated” group based on a two-side alpha 0.05 chi-square test with N=135 per group. This assumes that the proportion of infants with apnea will be 15% in the “unvaccinated” group and 2-fold higher (30%) in the “vaccinated” group. This assumption is based on a review of the literature and expert opinion. The study allows for a 10% dropout rate to give a total sample of 300 infants.

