#### **8.4 Postmenstrual age (PMA) Evaluation**

Study objectives PO1, SO1, SO2, EO2.1, EO2.2, EO3.1, and EO3.2 will be presented and evaluated between groups by postmenstrual age group (PMA <37 weeks /  $\geq$ 37 weeks). PMA will be defined as the sum of gestational age plus postnatal age. PO1, SO2, and EO3 are categorical with either no event or 1 or more events, and will be presented and compared using a Mantel- Haenszel statistic by PMA group at the two-sided alpha 0.05 level. The stratified odds ratio and corresponding 95% confidence interval for the occurrence will also be calculated. SO1 and EO2 are count data and will be compared using a Poisson regression model with study site as covariates by PMA group. These tests will be performed at the alpha 0.05 level.

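### The primary apnea comparison is valid but leaves collected baseline information unused; adjusting for it could add about 0 to 8 points of power, depending on a prognostic strength the documents do not give

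*SAP*

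**What the plan says.** SAP 8.1 has the proportions with at least one apneic event "compared using a Mantel-Haenszel statistic in a stratified analysis by study site and gestational age to control for the randomization blocks", and adds a stratified odds ratio with 95% CI. Gestational age enters as the two randomization levels, below 28 weeks and 28 weeks or more (SAP 4.3). No other covariate enters, and no sensitivity analysis in SAP 9 adds one.

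SAP 7.1 lists postmenstrual age, respiratory support and supplemental oxygen on the day of randomization, and "caffeine use on the day of randomization", all as descriptive baseline data. SAP 8.4 takes postmenstrual age further: the primary objective and several others "will be presented and evaluated between groups by postmenstrual age group", split at 37 weeks.

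On prognosis, Protocol 1.1 says that some cited studies found lower gestational age and greater disease severity to be risk factors. Its Table 2 gives, for one retrospective study of 497 infants, "Younger postnatal age Lower birth weight More severe clinical illness". Other rows name longer ventilation, chronic lung disease, longer prior CPAP and cardiorespiratory symptoms persisting at immunization. No strength of association is given, and caffeine does not appear.

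The power statement in SAP 4.2 is "based on a two-side alpha 0.05 chi-square test with N=135 per group", with no covariates.

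**The concern.** The planned sample yields few events. Expected apnea cases are 135 × 0.15 + 135 × 0.30 = 20.25 + 40.5, or about 61. With so few, chance imbalance between arms in a real predictor of apnea adds noise that a pre-specified adjustment would remove without recruiting anyone.

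Interval width matters here as well as the test. A result showing no clear excess of apnea would be read as evidence on vaccine safety, and how far it excludes an excess depends on the interval. If the baseline variables do predict apnea, the planned analysis gives up some power and some precision on the absolute-risk scale.

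**Working it through.** **1. The plan's own figure.** Inputs from SAP 4.2: "the proportion of infants with apnea will be 15% in the “unvaccinated” group", "2-fold higher (30%) in the “vaccinated” group", 135 per arm, two-sided alpha 0.05. With the pooled chi-square formula:

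- Mean risk 0.225; null SE = √(2 × 0.225 × 0.775 / 135) = 0.0508; critical difference = 1.96 × 0.0508 = 0.0996.
- Alternative SE = √((0.15 × 0.85 + 0.30 × 0.70) / 135) = 0.0500.
- Power = Φ((0.15 − 0.0996) / 0.0500) = Φ(1.008) = 84.3%.

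This reproduces the stated value. With 10% dropout, 270 / 0.90 = 300, also as stated.

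**2. What the gestational-age stratum leaves open.** SAP 8.4 defines postmenstrual age as gestational plus postnatal age. Protocol 4.1 admits gestational age below 33 weeks and postnatal age of 6 to 12 weeks. In the upper stratum, postmenstrual age can therefore run from 28 + 6 = 34 weeks to just under 33 + 12 = 45 weeks. The stratum captures it only in part.

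**3. Gain by formula.** Let R² be the share of outcome variance explained by the added covariates beyond the strata (not in the documents; assumed 0 to 0.20). The effective size per arm is 135 / (1 − R²), and the SE of a risk difference is multiplied by √(1 − R²).

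| R² | Effective n per arm | Power | SE multiplier |
|---|---|---|---|
| 0 | 135.0 | 84.3% | 1.00 |
| 0.02 | 137.8 | 85.0% | 0.99 |
| 0.05 | 142.1 | 86.1% | 0.975 |
| 0.10 | 150.0 | 87.9% | 0.949 |
| 0.20 | 168.8 | 91.3% | 0.894 |

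**4. Gain by simulation.** There were 4,000 trials per setting, each with 270 infants and marginal risks held at 15% and 30%. Sites were split 30/30/40%. Gestational-age strata were assumed 50/50, with an assumed logit effect of ±0.5. Three independent normal covariates had a joint logit-scale SD of s. The planned site-by-gestational-age test was compared with logistic regression on arm, site, gestational-age stratum and the three covariates.

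| s | R² | AUC of added covariates | Planned power | Adjusted power | SD of risk difference, strata only → adjusted | SD of log OR, planned → adjusted |
|---|---|---|---|---|---|---|
| 0 | 0 | 0.50 | 86.3% | 86.3% | 0.0484 → 0.0488 | 0.315 → 0.326 |
| 0.5 | 0.03 | 0.63 | 86.0% | 87.3% | 0.0484 → 0.0477 | 0.319 → 0.337 |
| 0.75 | 0.06 | 0.69 | 86.8% | 89.7% | 0.0492 → 0.0472 | 0.322 → 0.348 |
| 1.0 | 0.11 | 0.74 | 85.7% | 90.4% | 0.0490 → 0.0460 | 0.319 → 0.359 |
| 1.5 | 0.21 | 0.82 | 85.2% | 92.9% | 0.0511 → 0.0447 | 0.333 → 0.413 |

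Under the null, rejection rates were 5.0 to 5.6% for the planned test and 4.9 to 5.1% for the adjusted one. Each power figure has a Monte Carlo SE of about √(0.86 × 0.14 / 4,000) = 0.5 points, so the comparison within a row is what matters.

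**5. Cost in degrees of freedom.** Protocol 5.4 lists five support modes, and Protocol 4.2 excludes or delays infants on NIPPV, which leaves four. A model with arm (1), site (2), gestational-age stratum (1), postmenstrual age (1), caffeine (1) and four-level support (3) has 9 coefficients, or 61 / 9 = 6.8 events each. A separate simulation of a full model with four-level support gave planned versus adjusted power of 85.6 versus 85.4% with no information, 86 versus 88–89% at modest strength and 86 versus 91–94% at strong strength. Type I error was about 5 to 6%.

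**6. Effect measure.** At s = 1.0 the mean log odds ratio moves from 0.93 (planned) to 1.11 (adjusted), while its SD rises from 0.319 to 0.359. Power rises because the conditional odds ratio lies further from 1; its interval is no narrower. The SD of the standardized risk difference falls: by 1 to 4% at s = 0.5 to 0.75, and by 6 to 12% at s = 1.0 to 1.5.

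**The case against.** The strongest reply is that this is a choice, not a defect. The planned test is valid, uses exactly the randomization strata, and reaches 84.3% power on the plan's assumptions without any covariate. That stands, and a reader should not infer that the primary analysis is wrong or underpowered on its own terms. The margin does depend on a full doubling, however. At 15% versus 27% (my assumption, for illustration) the same formula gives 67.9%, and 73.0% with R² of 0.11. The one randomized trial in Protocol Table 2 reported prolonged apnea in 16% of the DTaP group and 20% of controls.

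A second reply is that the evidence for prognosis is thin. This stands in part. A reader might infer that the trial treats all three variables as prognostic, but the documents go that far at most for postmenstrual age. For respiratory status, Table 2 mainly names history and severity, not support at randomization, and excluding ventilated and NIPPV infants narrows that variable. Caffeine is only collected.

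A third is that SAP 8.4 already deals with postmenstrual age. It does not: results by subgroup give no adjusted overall comparison.

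A fourth concerns timing, and it stands. Protocol 5.4 records respiratory support at randomization in the unvaccinated arm but at vaccination in the vaccinated arm, which may be up to 12 hours after randomization. SAP 7.1 says only the day of randomization. Adjusting for the value as recorded would bring a post-randomization variable into one arm.

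**Conclusion.** The concern holds as a missed gain in efficiency, not an error. The expected change in power is about 0 points with no prognostic information, 1 to 3 points at weak to modest strength (R² about 0.03 to 0.06) and 4 to 8 points at strong strength (R² about 0.11 to 0.21). No single value can be claimed, because the documents give no prognostic strength. The figures also rest on 270 analyzed infants, the plan's 15% and 30%, and the assumed site and gestational-age mix.

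It would be tempting to say that adjustment makes the reported result more precise. That is true only for an absolute measure such as a standardized risk difference. SAP 8.1 reports an odds ratio, and the spread of the log odds ratio increases under adjustment. If the covariates prove uninformative, the loss is negligible: power changes by 0.2 points or less in both simulations, and the risk-difference SD grows by about 1%.

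**What to change.** Before unblinded analysis, pre-specify in SAP 8.1 a covariate-adjusted analysis of the primary objective:

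- **Model:** logistic, with arm, site, gestational-age stratum, continuous postmenstrual age at randomization, and coarsely coded respiratory support and caffeine use. Two-level support gives 7 coefficients, or 61 / 7 = 8.7 events each. Extra Mantel-Haenszel strata are not a substitute: three further binary factors would make 6 × 8 = 48 cells, with about 270 / 48 = 5.6 infants each.
- **Timing:** use only values fixed at or before randomization in both arms. If support exists only as the at-vaccination value in the vaccinated arm, leave it out.
- **Reporting:** a standardized risk difference with 95% CI, alongside the planned Mantel-Haenszel test and stratified odds ratio. If the sponsor keeps Mantel-Haenszel as primary, make this a named supporting analysis.
- **Test:** state a robust or small-sample-checked method, since a likelihood-ratio test can run slightly above 5% at this event count.

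The cost is SAP wording, one more model, a second effect measure beside the odds ratio adopted in SAP version 4.0, and possibly re-abstraction of support at randomization for the vaccinated arm. No extra infants are needed.

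In the same edit, reconcile the strata: Protocol 6.2.2.3 stratifies the comparison by site only, and SAP 8.1 by site and gestational age.
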